Appendix 2: Examination Procedures, Tests, Equipment, and Techniques60

Appendix 3: Protocol Amendment Summary70

Appendix 4: Sponsor [REDACTED] Approvals	95
Appendix 5: Investigator's Signature	97

LIST OF ABBREVIATIONS

AE	adverse event
BCVA	best-corrected visual acuity
BID	twice daily
<hr/>	
CRO	Contract Research Organization
DED	Dry Eye Disease
DHHS	Department of Health and Human Services
eCRF	electronic case report form
EKG	electrocardiograph
ERC	ethical review committee
ETDRS	Early Treatment of Diabetic Retinopathy Study
FDA	Food and Drug Administration
GCP	Good Clinical Practice
HIPAA	Health Information Portability and Accountability Act
ICF	informed consent form
ICH	International Council for Harmonisation
IND	investigational new drug application
IP	investigational product
IOP	intraocular pressure
IRB	institutional/independent review board
IUD	intra uterine device
IWRS	Interactive Web Response System
LASIK	laser in situ keratomileusis
logMAR	logarithm of the minimum angle of resolution
LPS	lipopolysaccharide
LTFU	Long-Term Follow-up
MDA	malonyldialdehyde
MedDRA	Medical Dictionary for Regulatory Activities
MGD	meibomian gland dysfunction
mm	millimeter
µL	microliter
mmHg	millimeters of mercury
OD	right eye
OS	left eye
OTC	over-the-counter
QID	four times daily
RASP	reactive aldehyde species
SAE	serious adverse event
TEAEs	treatment emergent adverse events
TMF	Trial Master File
VA	visual acuity
WHO	World Health Organization

1 INTRODUCTION

Dry eye disease (DED) is a complex and chronic condition characterized by ocular discomfort, visual disturbance, tear film instability, increased tear osmolarity, and inflammation of the ocular surface that, in severe cases, can lead to loss of vision (Dry Eye Workshop 2007). Although estimates of the prevalence of dry eye disease vary considerably depending on the criteria used to define the disease, as many as 3.2 million women and 1.7 million men over the age of 50 are thought to have DED in the United States, and prevalence is projected to increase by 40% by 2030 as a result of population aging and increasing computer use (Schaumberg 2002, Schaumberg 2003, Schaumberg 2009, Brewitt 2001).

Reactive aldehyde species (RASP) are reactive organic molecules that bind to proteins, carbohydrates, lipids, and nucleic acids (Esterbauer 1991). RASP that are not sequestered or otherwise protected in specific metabolic processes are toxic, and aldehyde binding to cellular constituents leads to inflammation via activation of NF κ B and other pro-inflammatory mediators (Yadav 2013), molecular dysfunction (O'Brien 2005), and the accumulation of indigestible metabolites, such as lipofuscin components in the retina (Boyer 2012).

In biological systems, RASP are formed by a variety of processes, including the oxidation of alcohols, polyamine and glucose metabolism, and oxidative stress. In non-disease states, levels of RASP are low due to the near ubiquitous presence of aldehyde dehydrogenases and other enzymes that catabolize aldehydes. However, in disease states, the capacity of aldehyde dehydrogenases to neutralize toxic aldehydes is exceeded, resulting in increased RASP levels. Elevation in the levels of RASP, particularly malonyldialdehyde (MDA), has been described in a variety of inflammatory ocular diseases, including pterygium, Behcet's Disease, Sjögren's Syndrome, anterior uveitis, and dry eye disease (Sandikci 2003, Cejkova 2007, Balci 2011, Turk 2014, Choi 2016, Augustin 1995).

Reproxalap is a novel small molecule, formulated for topical ophthalmic delivery that functions as a RASP sequestering agent, or "trap," which binds rapidly and irreversibly to RASP. By irreversibly trapping RASP, reproxalap is expected to diminish inflammation thought to be caused or exacerbated by elevated RASP levels in inflammatory ocular conditions. Reproxalap has demonstrated anti-inflammatory effects in numerous ocular and non-ocular preclinical models of inflammation:

- In a rat model of lipopolysaccharide (LPS)-induced uveitis, topical ocular dosing of reproxalap significantly reduced inflammatory ocular effects and significantly reduced ocular levels of two pro-inflammatory cytokines.
- In a rabbit ocular healing study, topical ocular reproxalap significantly reduced haze intensity and reduced the rate of haze development following photorefractive keratectomy.
- In a model of LPS-induced systemic inflammation, a single intraperitoneal dose of reproxalap led to a significant reduction in levels of several pro-inflammatory cytokines, while also increasing levels of the anti-inflammatory cytokine IL-10.

- In a phorbol 12-myristate-13-acetate-induced mouse model of contact dermatitis, intraperitoneal administration of reproxalap significantly reduced edema.
- In an oxazolone-induced, delayed-type hypersensitivity mouse model, intraperitoneal administration of reproxalap significantly reduced edema and resulted in statistically significant reduction of tissue cytokines at the site of inflammation.
- In a mouse model of lung inflammation, intraperitoneal administration of reproxalap reduced infiltration of inflammatory cells and protein in the lung, and resulted in reductions in levels of pro-inflammatory cytokines.
- In a model of radiation-induced mucositis in hamsters, subcutaneous administration of reproxalap significantly improved healing time and reduced fibrosis (scarring).

In 1995, Augustin et al. (Augustin 1995) described elevations in tear MDA levels that correlated with severity in DED patients. Subsequently, Choi et al. (Choi 2016) reported that expression of MDA and 4-hydroxynonenal (another RASP commonly associated with inflammation) is increased in the tear film and ocular surface of patients with DED. Consistent with the literature that supports the notion that RASP mediate pro-inflammatory toxicity in DED, the anti-inflammatory effects of the RASP scavenger reproxalap have been demonstrated in Phase 2 clinical trials in DED, noninfectious anterior uveitis (Mandell 2020), and allergic conjunctivitis. In aggregate, a broad array of preclinical and clinical evidence supports the use of reproxalap for the treatment of ocular inflammation, including DED.

2 STUDY OBJECTIVES

The objective of this study is to compare the safety of topical ocular 0.25% reproxalap to vehicle in patients with dry eye disease.

3 CLINICAL HYPOTHESES

N/A

4 OVERALL STUDY DESIGN

The ADX-102-DED-021 clinical trial is a Phase 3, multicenter, randomized, double-masked, parallel-group, vehicle-controlled design. Subjects will be randomized to one of the following treatment groups at Visit 2:

[figure not shown]
- 0.25% Reproxalap Ophthalmic Solution (reproxalap)
- Vehicle Ophthalmic Solution (vehicle)

[figure not shown]
Approximately 850 subjects will be randomly assigned to one of the two treatment groups (2:1) to receive either reproxalap or vehicle as topical ophthalmic drops administered bilaterally QID for four weeks followed by BID dosing for weeks 5-6. Approximately 550 subjects will dose QID for four weeks and continue dosing BID for the following 11 months. Subjects, Sponsor, CRO, and site personnel will be masked to treatment assignment.

All subjects will dose with randomized treatment QID between Visit 1 and Visit 2 and switch to BID dosing between Visit 2 and Visit 4 or between Visits 2 and Visit 7 for the long-term follow-up group.

The total number of expected participants, including screen failures, is approximately 1050 subjects.

A study flow chart appears below:

Subjects who terminate early during the treatment period will be asked to complete safety assessments prior to commencement of alternative DED therapy (if possible). [REDACTED]

[REDACTED]

5 STUDY POPULATION

5.1 Number of Subjects (approximate)

It is estimated that approximately 1050 subjects will be screened to enroll approximately 850 subjects in a 2:1 ratio of reproxalap to vehicle. Approximately 550 subjects will continue after Week 6 for long-term follow-up, with the goal of at least 100 reproxalap subjects completing the long-term follow-up.

5.2 Study Population Characteristics

All subjects must be at least 18 years of age, of either gender, and of any race, and must meet all inclusion criteria and none of the exclusion criteria.

5.3 Inclusion Criteria

Subjects must meet all of the following criteria:

[figure not shown]
1. At least 18 years of age (either gender and any race);
2. Ability to provide written informed consent and sign the Health Information Portability and Accountability Act (HIPAA) form;
3. Reported history of dry eye for at least 6 months prior to Visit 1;
4. History of use or desire to use eye drops for dry eye symptoms within 6 months of Visit 1;

5.4 Exclusion Criteria

[figure not shown]
Subjects must not meet any of the following criteria:

1. Clinically significant slit lamp findings at Visit 1 that may include active blepharitis, meibomian gland dysfunction (MGD), lid margin inflammation, or active ocular allergies that require therapeutic treatment, and/or in the opinion of the investigator may interfere with study parameters;
2. Diagnosis of an ongoing ocular infection (bacterial, viral, or fungal), or active ocular inflammation at Visit 1;
3. Contact lens use within 7 days of Visit 1 or anticipate using contact lenses during the trial;
4. Eye drop use within 2 hours of Visit 1;
5. Previous laser-assisted in situ keratomileusis (LASIK) surgery within the last 12 months;

7. Planned ocular and/or lid surgeries over the study period or any ocular surgery within 6 months of Visit 1;
8. Temporary punctal plugs during the study that have not been stable within 30 days of Visit 1;

9. Use of and unwillingness to discontinue topical ophthalmic prescription (including medications for glaucoma) or over-the-counter (OTC) solutions, artificial tears, gels or scrubs for the duration of the trial (excluding medications allowed for the conduct of the trial);

11. Pregnancy, nursing, or planned pregnancy during the conduct of the trial;
12. Unwillingness to submit a urine pregnancy test at Visit 1 and Visit 3 (6-week subjects)/Visit 7 (LTFU subjects) (or early termination visit) if of childbearing potential. (Nonchildbearing potential is defined as a woman who is permanently sterilized [e.g., has had a hysterectomy or tubal ligation], or is post-menopausal [without menses for 12 consecutive months];
13. If of childbearing potential, unwillingness to use an acceptable means of birth control. (Acceptable methods of contraception include: hormonal – oral, implantable, injectable, or transdermal contraceptives; mechanical – spermicide in conjunction with a barrier such as a diaphragm or condom; intrauterine device [IUD]; or surgical sterilization of partner. For non-sexually active males or females, abstinence may be regarded as an adequate method of birth control; however, if the subject becomes sexually active during the study, he/she must agree to use adequate birth control as defined above for the remainder of the trial.);
14. Known allergy and/or sensitivity to the test article or its components;
15. A condition or be in a situation which the investigator feels may put the subject at significant risk, may confound the study results, or may interfere significantly with the subject's participation in the study;
16. Abnormal endothelial cell count (LTFU subjects only);
17. Current enrollment in an investigational drug or device study or have used an investigational drug or device within 30 days of Visit 1;
18. Previous reproxalap use within the past year; Inability or unwillingness to follow instructions, including participation in all study assessments and visits.

5.5 Withdrawal Criteria (if applicable)

If at any time during the study the investigator determines that a subject's safety has been compromised, the subject may be withdrawn from the study.

Subjects may withdraw consent from the study at any time.

Sponsor and/or investigator may discontinue any subject for non-compliance or any valid medical reason (see Section 8.6.2).

6 STUDY PARAMETERS

6.1 Primary Safety Endpoints

- Proportion of subjects that experience at least one TE-SAE of a visual acuity decrease (defined as an increase of 0.22 or greater in logMAR score) categorized as probably or definitely related to IP
- Proportion of subjects that experience at least one TE-SAE of an IOP increase from baseline of ≥ 10 mm Hg AND report an IOP of > 25 mm Hg categorized as probably or definitely related to IP
- Proportion of subjects that experience at least one TE-SAE of the cornea detected via slit-lamp biomicroscopy categorized as probably or definitely related to IP
- Proportion of subjects that experience at least one TE-SAE of the retina detected via fundoscopy categorized as probably or definitely related to IP

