Study Formulations and Formulation Numbers:	0.25% Reproxalap Ophthalmic Solution Vehicle Ophthalmic Solution
Evaluation Criteria	
Primary Safety Endpoints	
Proportion of subjects that experience at least one treatment-emergent severe adverse event (TE-SAE) of a visual

	
acuity decrease (defined as an increase of 0.22 or greater in logMAR score) categorized as probably or definitely related to Investigational Product (IP)
 
• Proportion of subjects that experience at least one TE-SAE of an IOP increase from baseline of ≥ 10 mm Hg AND report an IOP of > 25 mm Hg categorized as probably or definitely related to IP• Proportion of subjects that experience at least one TE-SAE of the cornea detected via slit-lamp biomicroscopy categorized as probably or definitely related to IP• Proportion of subjects that experience at least one TE-SAE of the retina detected via fundoscopy categorized as probably or definitely related to IP
Safety Evaluation Criteria:	
• Visual acuity• Slit-lamp evaluation• Adverse event query• Intraocular Pressure (IOP)• Dilated fundoscopy• Central Cornea Endothelial Cell Counts (1-year LTFU subjects)• Blood chemistry and hematology analysis in a subset of subjects (1-year LTFU subjects only)• Unanesthetized Schirmer's Test 

Other Measures:	
• Urine Pregnancy Test
General Statistical Methods and Types of Analyses	
Analysis Populations	

• Safety Population – The Safety population will include all subjects receiving treatment from whom at least one safety measurement is obtained following the first dose of study drug. The Safety population will be analyzed for all safety assessments. Subjects in the Safety population will be analyzed as treated.	

- **Safety-LTFU Population** – The Safety population will include all LTFU subjects receiving treatment from whom at least one safety measurement is obtained following the first dose of study drug. The Safety-LTFU population will be analyzed for all safety assessments. Subjects in the Safety-LTFU population will be analyzed as treated.

Sample Size

[figure not shown]
[figure not shown]
[figure not shown]
[figure not shown]

Table 1: Assumed True Event Proportions

[figure not shown]
[figure not shown]

[figure not shown]

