Other safety endpoints will be summarized by treatment group and visit using descriptive statistics using the Safety population or Safety-I.TFU population. Changes or shifts from baseline will also be summarized where appropriate. Assessments performed by eye will be summarized separately for right eye (OD) and left eye (OS).

For quantitative safety endpoints, comparisons between treatment groups will be made at the eye level. [REDACTED]

[REDACTED]

Summary of Known and Potential Risks and Benefits to Human Subjects

There are no known safety risks of topical ocular reproxalap, which has been administered to 968 subjects across 8 Phase 2 and Phase 3 clinical trials in concentrations of 0.1%, 0.25%, and 0.5%, up to 4-times-daily for 12 weeks and 8-times-daily tapered to 4-times-daily over 4 weeks in healthy volunteers and in subjects with dry eye disease, allergic conjunctivitis, and noninfectious anterior uveitis. No consistent changes in visual acuity, slit-lamp evaluation, IOP, dilated fundoscopy, or non-ocular adverse events have been observed. No treatment-related serious adverse events have been observed. [REDACTED]

[REDACTED]

Reproxalap has demonstrated consistent, statistically significant, and clinically meaningful activity in dry eye disease, allergic conjunctivitis, and noninfectious anterior uveitis as assessed by change from baseline and improvement over vehicle.

TABLE OF CONTENTS

SYNOPSIS	4
TABLE OF CONTENTS	16
LIST OF ABBREVIATIONS	20
1 INTRODUCTION	21
2 STUDY OBJECTIVES	22
3 CLINICAL HYPOTHESES	22
4 OVERALL STUDY DESIGN	22
5 STUDY POPULATION	24
5.1 Number of Subjects (approximate)	24
5.2 Study Population Characteristics	24
5.3 Inclusion Criteria	25
5.4 Exclusion Criteria	25
5.5 Withdrawal Criteria (if applicable)	26
6 STUDY PARAMETERS	27
6.1 Efficacy Measures	27
6.2 Safety Measures	27
6.3 Other Measures	27
7 STUDY MATERIALS	28
7.1 Study Drug(s)	28
7.1.1 Study Drug(s)/ Formulation(s)	28
7.1.2 Study Drug Packaging Configuration	28
7.1.3 Study Drug Storage and Accountability	28
7.1.4 Instructions for Dispensation, Use, and Administration	28
7.2 Other Study Supplies	29
8 STUDY METHODS AND PROCEDURES	29
8.1 Subject Entry Procedures	29
8.1.1 Overview	29
8.1.2 Informed Consent	29
8.1.3 Washout Intervals	29
8.1.4 Procedures for Final Study Entry	29
8.1.5 Methods for Assignment to Treatment Groups:	29
8.2 Concurrent Therapies	30

8.2.1	Prohibited Medications/Treatments	30
8.2.2	Escape Medications	30
8.2.3	Special Diet or Activities	30

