9.2 Serious Adverse Events

An adverse event is considered serious if, in the view of either the investigator or sponsor, it results in any of the following outcomes:

- Death;
- A life-threatening adverse event;

Note: An adverse event is considered "life-threatening" if, in the view of either the investigator or sponsor, its occurrence places the patient or subject at immediate risk of death. It does not include an adverse event that, had it occurred in a more severe form, might have caused death.

- Inpatient hospitalization or prolongation of existing hospitalization;

Note: The term "inpatient hospitalization" refers to any inpatient admission (even if less than 24 hours). For chronic or long-term inpatients, inpatient admission includes transfer within the hospital to an acute/intensive care inpatient unit. Inpatient hospitalization does not include: emergency room visits; outpatient/same-day/ambulatory procedures; observation/short stay units; rehabilitation facilities; hospice facilities; nursing homes; or clinical research/phase 1 units.

Note: The term "prolongation of existing hospitalization" refers to any extension of an inpatient hospitalization beyond the stay anticipated or required for the reason for the initial admission as determined by the investigator or treating physician.

- A persistent or significant incapacity or substantial disruption of the ability to conduct normal life functions;

Note: A serious adverse event specifically related to visual threat would be interpreted as any potential impairment or damage to the subject's eyes (e.g., hemorrhage, retinal detachment, central corneal ulcer or damage to the optic nerve).

- A congenital anomaly/birth defect.

Important medical events that may not result in death, are life-threatening, or require hospitalization may be considered serious when, based upon appropriate medical judgment, they may jeopardize the patient or subject and may require medical or surgical intervention to prevent one of the outcomes listed in this definition.

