10.4.6 Other Safety Analyses

Dosing information will be summarized overall subjects and listed for each subject will be listed. Discontinuation of treatment will be summarized by treatment received. The primary reason for trial drug discontinuation will also be summarized by treatment received.

Adverse events (AEs) will be coded using the MedDRA dictionary. An AE is treatment emergent if it occurs or worsens after the first dose of study treatment.

Frequencies and percentages of subjects with treatment-emergent adverse events (TEAEs), serious TEAEs, and TEAEs causing premature treatment discontinuation will be provided by treatment group. Furthermore, frequencies will be given of subjects with TEAEs by system organ class and preferred term for the following categories of AEs:

- All TEAEs
- TEAEs at least possibly related to study treatment
- TEAEs leading to study treatment discontinuation
- Serious TEAEs
- By maximal severity
- By study day of onset

Separate analyses will be performed for ocular and non-ocular AEs. Separate analyses of AEs will be generated for the Safety population with 6 weeks of follow-up and the Safety-LTFU population with 6 months of follow-up (or 1 year of follow-up).

Other safety endpoints will be summarized by treatment group and visit using descriptive statistics. Changes or shifts from baseline will also be summarized where appropriate. Separate analyses will be generated for the Safety population with 6 weeks of follow-up and the Safety-LTFU population with 6 months of follow-up (or 1 year of follow-up).

Assessments performed by eye will be summarized separately for right eye and left eye.

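### The primary visual acuity and IOP endpoints count a threshold crossing only if it is also a TE-SAE rated probably or definitely related, and no readable analysis counts the measured crossings themselves

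*Combined protocol and SAP*

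**What the plan says.** Section 6.1 sets two primary endpoints on measured quantities. One counts subjects with "at least one TE-SAE of a visual acuity decrease (defined as an increase of 0.22 or greater in logMAR score"). The other counts subjects with "at least one TE-SAE of an IOP increase from baseline of ≥ 10 mm Hg AND report an IOP of > 25 mm Hg". Both add that the event must be "categorized as probably or definitely related to IP". The same form recurs in the synopsis, the hypotheses (10.2) and the primary estimand (10.4.5).

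The synopsis expands the term as "treatment-emergent severe adverse event (TE-SAE) of a visual" acuity decrease, that is, *severe*. The list of abbreviations expands SAE as "serious adverse event". Section 9.1.1 makes severity a qualitative judgement by the investigator or as reported by the subject. Section 9.2 makes seriousness a judgement of the investigator or sponsor against listed outcomes, among them "A persistent or significant incapacity or substantial disruption of the ability to conduct normal life functions". Section 9.1.2 leaves causality to the investigator.

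Measured VA and IOP are listed as other safety endpoints in 6.2. Section 10.4.6 states: "Other safety endpoints will be summarized by treatment group and visit using descriptive statistics". It adds changes or shifts from baseline where appropriate, by eye. Section 10.4.1 includes the minimum and maximum among the summary statistics. The synopsis adds eye-level comparisons between arms for quantitative safety endpoints; the text that follows is redacted.

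**The concern.** The protocol names the VA and IOP changes it regards as important and lists both measurements as safety assessments. The primary endpoints nevertheless do not count those changes. They count adverse events that reach a given grade and causality rating and that also meet the threshold. A reversible 0.22 logMAR loss, or an IOP that goes from 16 to 26 mm Hg at one visit, meets the numeric criterion. It could still be recorded as a mild or moderate, non-serious event, or rated only possibly related, and then it does not count.

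The sole objective is to compare safety. If few crossings pass both filters, the primary comparison could show close to no events in either arm, and a finding of no difference would describe the filters as much as VA or IOP.

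**Working it through.** **1. The plan's own alpha figures.** The synopsis allots 0.0165 to the 6-week family and 0.0335 to the long-term family: 0.0165 + 0.0335 = 0.05. Four 6-week endpoints under Bonferroni: 0.0165 / 4 = 0.004125. Both reproduce exactly. The assumed event proportions and the sample-size text are not shown, so power cannot be reproduced.

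**2. Is a crossing automatically a TE-SAE?**
- Section 9.1 requires clinically relevant deterioration to be recorded as an adverse event and gives no numeric trigger.
- The severity scale in 9.1.1 and the VA and IOP procedures in Appendix 2 are not shown.
- Section 9.2 contains no VA or IOP threshold.
- The VA wording could be read as making the crossing itself the event. The IOP wording contains no such definition. On either reading the causality rating still applies.

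**3. Does another readable analysis count crossings?**
- By-visit, by-eye summaries show the extremes but not how many subjects crossed at any visit in either eye.
- Eye-level comparisons of quantitative measures are not per-subject counts.
- Adverse-event tables count what was recorded as an event, not what was measured.
- The sensitivity analyses in 10.4.5 vary the handling of intercurrent events or use incidence rates. None is described as lifting the TE-SAE condition.

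**4. Arm sizes (2:1).** 850 × 2/3 ≈ 567 reproxalap and 283 vehicle. Long-term: 550 × 2/3 ≈ 367 and 183.

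**5. Events needed for significance.** The test is not readable, so a two-sided Fisher exact test is assumed, with no vehicle events.

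| Population | Alpha | Fewest reproxalap events |
|---|---|---|
| 6 weeks, 567 vs 283 | 0.004125 | 15 (2.6%), p = 0.0038; 14 gives p = 0.0070 |
| Long-term, 367 vs 183 | 0.0335 / 4 = 0.008375 (split assumed) | 13, p = 0.0063 |
| Long-term, 367 vs 183 | 0.0335 unsplit | 9, p = 0.0331 |

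**6. Events to expect, *serious* reading only.** The synopsis reports 968 exposed subjects and states: "No treatment-related serious adverse events have been observed". The one-sided 95% upper limit is 1 − 0.05^(1/968) = 0.00309, or 0.31%. Then 567 × 0.00309 ≈ 1.8. This is an upper limit, covers all types of related serious event together, and is far below 15.

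**7. Illustration of what filtering costs.** The crossing rates and capture shares below are assumptions, not document figures. Capture is the share of crossings that are both classed as TE-SAEs and rated probably or definitely related. The entries are Fisher power at 567 vs 283 and two-sided 0.004125.

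| True crossing rates (reproxalap vs vehicle) | All counted | 75% captured | 50% | 25% | 10% |
|---|---|---|---|---|---|
| 10% vs 3% | 84% | 64% | 35% | 8% | about 0% |
| 8% vs 3% | 50% | 31% | 14% | 2% | about 0% |
| 6% vs 2% | 40% | 23% | 10% | 1% | about 0% |

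**The case against.** A reader might infer that most measured crossings are lost. The documents give neither a crossing rate nor a capture share, so *most* has no support. The note in 9.2 on visual threat extends seriousness to potential impairment of the eye. Its examples are grave, but the wording is broad enough that some 0.22 logMAR losses could qualify.

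A reader might also infer that large individual changes vanish from the report. They need not. Where change is summarised with its minimum and maximum, the extreme value appears for each arm, eye and visit. Quantitative measures are compared between arms at eye level. Treatment-emergent events are tabulated by arm, preferred term and maximal severity whatever their attribution. The exclusion concerns the formal primary test only.

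The 0-in-968 figure has limits. It counts related serious events, so it mixes the grade and causality filters. It says nothing on the *severe* reading. It comes from reproxalap exposure at several concentrations, with healthy volunteers included and the longest stated regimen 12 weeks, so it supports no statement about the vehicle arm or about one year.

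Finally, redacted or missing text could hold an automatic trigger or a threshold count, and the protocol gives the SAP precedence on statistical matters. The row labels in Appendix 1 are missing, so the visits at which VA and IOP are measured cannot be confirmed.

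All of these limits stand. None of them alters the endpoint wording, which leaves out any crossing that fails either filter.

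**Conclusion.** The point holds for the formal primary comparison. As worded, a VA or IOP crossing counts only if it is classed as a TE-SAE and rated probably or definitely related, so an unknown, possibly large, share of measured crossings is left out. No readable passage plans a per-subject count of crossings.

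The size can be bounded on the *serious* reading alone: at most about 1.8 expected events in about 567 reproxalap subjects, against at least 15 needed with none on vehicle. That rests on earlier exposure being a fair guide to this trial and on a Fisher-type test. On that reading a null result would say little about VA or IOP. On the *severe* reading the event rate is unknown, but both filters still apply. The power table shows only how quickly filtering can remove information; it does not estimate what this trial would lose.

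**What to change.** Keep the four primary endpoints and the alpha scheme. Unless the SAP already contains it, pre-specify in 10.4.5 or 10.4.6 a supportive analysis of the proportion of subjects with a measured crossing in either eye at any post-baseline visit, whether scheduled, unscheduled or early termination:

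- VA: logMAR increase from baseline of 0.22 or more.
- IOP: rise from baseline of 10 mm Hg or more with IOP above 25 mm Hg, both conditions in the same eye.

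Count crossings regardless of adverse-event status, grade or attribution. Report the arm difference with its 95% CI at 6 weeks (Safety) and at 6 months and 1 year (Safety-LTFU), outside the alpha-controlled tests. Present it beside the TE-SAE result when VA and IOP safety is interpreted. Use one expansion of TE-SAE throughout, so that the reader knows which filter the primary endpoint applies.

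The cost is SAP wording and two derived variables from measurements already listed as safety endpoints. The downside is that some crossings will be measurement noise or unrelated to treatment; under masking and randomisation these are expected in both arms alike.
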